- If 72 hours after final dose escalation, there is no further improvement in SCr, continuation of terlipressin is at the discretion of the Principal Investigator at the clinical site.
- If a subject is initiated on RRT, terlipressin can be continued for a maximum of 72 hours after initiation of RRT.
- Terlipressin must be discontinued when the subject is to undergo liver transplantation, TIPS, or any other vasopressor therapy (single administration of vasopressor for cardiac stress test is acceptable)
- Dosing must be permanently discontinued if an event of cardiac ischemia or mesenteric ischemia occurs.

Retreatment:

If judged by the investigator to be potentially beneficial, subjects who demonstrate at least a partial response during the initial treatment course (at least 50% reduction in SCr) and develop recurrence of HRS-AKI may be retreated for a maximum of 14 days. To qualify for retreatment the subject must again meet the study inclusion/exclusion criteria. Retreatment may occur within 90 days of the subject's first dose of terlipressin.

Duration of Treatment:

For the Prospective Terlipressin Group, the active treatment period will be up to 14 days, allowing 1 retreatment cycle.

For both Prospective and Retrospective Subjects:

All subjects will be followed:

Post treatment clinical data collection will be through phone call and chart review. Creatinine, BUN and eGFR will be recorded per standard of care, recording mortality and the date of last dialysis (CVVH or HD) session for the following time points:

Collaborative Research Study, Version 4: 06/29/21
To Treat HRS-AKI Patients with Continuous Terlipressin Infusion

Day 7 +/- 2 days;
Day 14 +/- 3 days;
Day 30 +/- 1 week and
Day 90 +/- 1 week
Day 180 +/- 2 weeks and
Day 365 +/- 2 weeks.

For subjects who have a liver transplant Post Treatment

If the subject has a liver transplant recorded prior to the 90-Day visit (phone call or chart review), additional follow up will occur through one year after liver transplant.

Creatinine, BUN and eGFR will be recorded per standard of care, recording mortality and the date of last dialysis (CVVH or HD) session for the following time points:

Day 0 (date of transplant) – record allocation MELD and last calculated MELD prior to transplant;
Day 7 +/- 2 days;
Day 14 +/- 3 days;
Day 30 +/- 1 week,
Day 90 +/- 1 week,
Day 180 +/- 2 weeks and
Day 365 +/- 2 weeks.

Key Efficacy and Safety Data Assessment:

Primary Efficacy Assessment:

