13.2 Secondary Efficacy Variables

- Improvement of renal function (SCr) from Day 1 through end of treatment, repeated measure analysis as compared to the Retrospective Control Group.
- For the Prospective Terlipressin Group alone and also in comparison to the Retrospective Control Group:
 - Incidence of dialysis by Day 30 and Day 90 of follow up.
 - Survival by Day 30 and Day 90 follow up.
 - Transplant by Day 30 and Day 90 follow up.
 - Serum creatinine at Day 30 and Day 90 follow up
 - Serum creatinine and incidence of dialysis at Day 30, Day 90, Day 180, and Day 365 after liver transplantation
 - Incidence of kidney transplant within one year after liver transplant
 - Descriptive analysis of number simultaneous liver kidney transplants and episodes of graft rejection at Day 90 and Day 365 after liver transplant

14 Serious Adverse Events

Only Serious Adverse Events will be collected for this study for the prospective group only. Safety review and assessments will be made only for the Prospective Terlipressin Group from time of first dose through 30 days after end of treatment. SAEs are collected from the start of study drug until 30 days after study drug was discontinued. Non-serious Adverse Events are not required to be collected for this study.

The investigator will record the nature, causality, severity, treatment, and outcome of the SAE, and will determine whether there is a “reasonable probability” that the study drug treatment caused the event.

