14.5 Study Drug Causality

Study drug causality will be assessed as follows:

Unrelated: An AE that is clearly and incontrovertibly due to extraneous causes (disease, environment, etc.) and does not meet the criteria for 'possible' or 'probable.'

Possible: The connection between the AE and study treatment appears unlikely but cannot be ruled out with certainty. An AE may be considered 'possibly related' if it has at least 2 of the following:

- It follows a reasonable temporal sequence from administration of study drug.
- It may readily have been produced by the subject's clinical state or by environmental or toxic factors.
- It follows a known response pattern to study drug.

Probable: An AE that is considered to be related to study drug treatment with a high degree of certainty. An AE may be considered probably related if:

- It follows a reasonable temporal sequence from administration of study drug.
- It cannot be reasonably explained by the known characteristics of the subject's clinical state.
- It follows a known pattern of response to study drug treatment.
- It reappears upon rechallenge.

Collaborative Research Study, Version 4: 06/29/21
To Treat HRS-AKI Patients with Continuous Terlipressin Infusion

Table 4 lists adverse events that are common in this subject population (i.e., with HRS), even in the absence of exposure to the study drug (Rozov-Ung and Panesar, 2010; Arroyo et al, 2008). The investigator may use this as a guidance while assessing the causality.

Table 4: Adverse Events Common to the Hepatorenal Syndrome (HRS) Population

MedDRA System Organ Class	Preferred Term
Blood and Lymphatic System Disorders	Anemia Coagulopathy
Cardiac Disorders	Atrial fibrillation Bradycardia
Gastrointestinal Disorders	Abdominal pain Diarrhea Nausea Vomiting
General Disorders and Administration Site Conditions	Multi-organ failure
Hepatobiliary Disorders	Hepatic failure
Infections and Infestations	Pneumonia Urinary tract infection
Metabolism and Nutrition Disorders	Hyperglycemia
Nervous System Disorders	Headache
Respiratory, Thoracic and Mediastinal Disorders	Dyspnea Epistaxis Pulmonary edema Respiratory failure
Vascular Disorders	Hypotension

Source: Rozov-Ung and Panesar, 2010; Arroyo et al, 2008.

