14.9 Hospitalizations

Planned hospital admissions and/or planned surgical operations for an illness or disease, which existed before the subject was randomized are not to be considered SAEs (e.g., re-hospitalization for liver transplantation). However, a baseline condition which deteriorates during the clinical study may be considered an SAE.

Following the initial hospital discharge, all re-hospitalizations within 30 days post end of treatment (except for planned hospital admissions or procedures as described above) are to be recorded as a SAE.

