15.4 Safety Variables

Safety variables will include the following:

- Serious adverse events and all deaths. Safety details may include:
 - Vital signs (body temperature, blood pressure, heart rate, respiratory rate, and SpO₂).
 - MELD score.
 - Encephalopathy score.
 - Laboratory parameters.

Serious Adverse events will be not classified by Medical Dictionary for Drug Regulatory Activities (MedDRA) system organ class, preferred term, severity, and seriousness. SAEs will be summarized using site reported terminology, as well as by the investigator's assessment of the relationship of the SAE to the study drug.

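### Section 15.4 summarizes SAEs to 30 days after end of treatment with no split at liver transplant, so surgical and on-drug events are mixed and only investigator causality separates them

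*Combined protocol and SAP*

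**What the plan says.** Section 14 sets the collection window: "SAEs are collected from the start of study drug until 30 days after study drug was discontinued". SAEs are the only adverse events collected, and only in the prospective terlipressin group.

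The synopsis, under Treatment Discontinuation, says "Terlipressin must be discontinued when the subject is to undergo liver transplantation".

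Section 15.4 says "SAEs will be summarized using site reported terminology", adds a summary by the investigator's assessment of relationship to study drug, and states that MedDRA coding will not be used. Section 15.6 defines the safety population as everyone dosed. No section splits, censors or tabulates SAEs by transplant.

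Section 14.9 excludes planned admissions and operations for a pre-existing illness from the SAE definition, with "re-hospitalization for liver transplantation" as its example. It does not exclude complications of the operation. Under section 14.3 an event that prolongs a hospital stay is serious, and under 14.9 unplanned readmissions within 30 days of end of treatment are to be recorded as SAEs.

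**The concern.** When treatment ends because the subject goes to transplant, the 30-day tail meant to catch late drug effects becomes the first 30 post-operative days. Serious events are to be expected after a liver transplant whatever drug preceded it. Ineligible subjects are capped at 25 of about 50, so about half or more of the group (50 − 25 = 25) are listed or transplant-eligible. Transplant inside the SAE window is thus a foreseeable event.

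Safety is part of the primary objective, and there is no control group against which to read the SAE summary. A table that runs straight through the transplant date cannot show how much was seen on drug, how much soon after it, and how much after surgery. Because terms are site-reported and uncoded, a reader cannot easily regroup them.

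The plan does treat transplant as a new starting point elsewhere. Table 2 counts follow-up days from transplant, and section 15.2 describes creatinine after transplant separately from creatinine in patients not transplanted. The SAE summary has no such separation.

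**Working it through.** The plan states no figure on this point, so there is none to reproduce. The check has two parts.

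**1. Share of the window that is post-operative**

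Inputs:
- Tail after last dose: 30 days (section 14).
- Days on drug in one course, T: 1 to 14 (14-day maximum, Table 1 and synopsis).
- Last dose at transplant (synopsis, Treatment Discontinuation).
- Survival to the end of the tail (assumption; an early death shortens the window).

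Formula: share = 30 / (T + 30).

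| Days on drug before transplant | Calculation | Post-operative share |
|---|---|---|
| 1 | 30/31 | 97% |
| 3 | 30/33 | 91% |
| 7 | 30/37 | 81% |
| 14 | 30/44 | 68% |

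So at least 68% of the window is post-operative for every single-course subject in this situation. If transplant comes g days after the last dose, the share is (30 − g)/(T + 30), which is smaller.

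Retreatment changes the result. The synopsis says subjects with a recurrence after at least a partial response "may be retreated for a maximum of 14 days". For two full courses with the second ending at transplant:
- both 30-day tails counted, no overlap: 30/(14 + 30 + 14 + 30) = 30/88 = 34%;
- only days on drug plus the last tail counted: 30/(14 + 14 + 30) = 30/58 = 52%.

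The documents do not say which count applies.

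**2. Whether the causality summary separates the two kinds of event**

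Section 14.5 lets an event be rated Possible if it meets at least two of three items. The first is "It follows a reasonable temporal sequence from administration of study drug". The second is that the patient's clinical state, or environmental or toxic factors, could readily have produced the event. A surgical complication within days of the last dose can meet both. Unrelated has two conditions: an unmistakably extraneous cause, and failure to meet the criteria for Possible or Probable. Read together, an event that meets those two items of Possible cannot be Unrelated, even if surgery is its obvious cause.

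**The case against.** The strongest reply is that the plan does not attribute surgery to the drug. Section 15.4 reports relatedness in the same sentence as the site terms, 14.5 has an Unrelated category, and 14.9 removes the planned transplant admission and operation. That stands. A reader might infer that surgery is counted as terlipressin harm; the documents do not support this. They support only that the events share one summary and that the filter between them is weak. The wording of Possible is also permissive, so investigators keep discretion, and site terms may themselves reveal a surgical complication.

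A reader might also infer that the SAE rate must rise with the proportion transplanted. Assume a 25% SAE risk before any transplant, 20–40% transplanted, and a 40–70% SAE risk after surgery. The pooled rate is then 0.8 × 0.25 + 0.2 × (1 − 0.75 × 0.6) = 31% at the low end and 0.6 × 0.25 + 0.4 × (1 − 0.75 × 0.3) = 46% at the high end. None of these inputs is in the documents. The formula also gives transplanted subjects the full 25% over 1–14 days when others have up to 44 days to reach it.

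Other assumptions reverse the direction. Subjects not transplanted keep accruing disease complications, which 14.10 requires to be recorded as SAEs where applicable. With a constant hazard giving 50% over 36 days, transplant on Day 6 and a 40% post-operative risk, the transplanted subject's risk is 1 − 0.5^(6/36) × 0.6 = 47%, below 50%.

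Finally, the synopsis allows unspecified additional analyses, and the dates are collected, so the split could be made later. That is true, but a table specified now is more credible than one chosen after the SAEs are known.

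**Conclusion.** The point holds in this form: the SAE summary runs through transplant without a split, and for a single course ending at transplant in a subject who survives 30 days, 68% to 97% of the window is post-operative. After retreatment the share can fall to 34% or 52%, depending on how the window is counted. The resulting mixture of surgical and on-drug events is separated only by a causality scale that can place a post-operative event in Possible and keep it out of Unrelated.

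These are shares of days, not of events. The documents give neither an SAE rate nor a transplant rate, so the effect on the overall SAE rate is unknown in size and in direction. The number of subjects whose treatment will end at transplant is also unknown. The plan should be changed on this point, but what is at stake is how interpretable the safety tables are; no prespecified safety test depends on it.

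**What to change.** Leave SAE collection and the all-period total as they are. Add one paragraph to section 15.4 that tabulates SAEs and deaths in three periods:

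- (a) first to last dose;
- (b) after last dose to the earlier of transplant or 30 days;
- (c) from transplant to 30 days after last dose.

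Give the number at risk and person-days for each, and show all three by transplant-eligible versus ineligible status. Person-days are essential because follow-up is so uneven. A subject transplanted at the end of 7 days on drug contributes 7, 0 and 30 days to (a), (b) and (c); one who stops after 7 days and is not transplanted contributes 7, 30 and 0. State in the same paragraph how the windows of a retreated subject are counted.

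Do not replace the overall summary with one censored at transplant. Such censoring would be informative, would move delayed drug effects out of the main table, and would set a few days of observation beside up to 44.

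No new data are needed. The transplant date is recorded (synopsis and Table 2), and SAE start and stop dates are requested whenever possible (section 14.12). The cost is one paragraph and extra tables, with small cells in about 50 subjects.

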8.4 Administration

Subjects in the Prospective Terlipressin Group:

Single-use, sterile 6-mL vials containing 1 mg of lyophilized terlipressin acetate (equivalent to 0.85 mg terlipressin free base) with 10 mg mannitol as a bulking agent/stabilizer.

- For initial bolus dose of 0.5mg, the vial will be reconstituted with 5 mL of sterile 0.9% sodium chloride solution and given over 1-minute push.
- Continued dosing will be by 2mg infusion per day for Days 1, and 2. For continuous infusion, the dose of terlipressin is to be dissolved in 0.9% sodium chloride solution and infused with a pump.
- If on Day 3 the SCr is not 30% lower from the baseline value, increase infusion dose to 4 mg per day.
- If on Day 5 the SCr is not 50% lower from the baseline value, increase infusion dose to 6-8 mg per day, per PI discretion. Dosing can be increased by more than 1 mg increment at Day 5 or beyond, up to a maximum of 8 mg/day.
- If the subject has infusion stopped for \geq 4 hours, a 0.5 mg bolus should be given prior to restarting infusion.
- The drug should not be used in subjects with severe coronary artery disease or in the setting of circulatory overload, pulmonary edema, or bronchospasm as determined by the Investigator. If drug therapy has been initiated, Investigator can also decide not to increase the dose, based on the patient's status with regard to the above, based on individual subject condition.

- If dosing is interrupted due to an adverse event, terlipressin may be re-started, at the discretion of the investigator, at the same or lower dose as per protocol. Terlipressin will not be restarted if dosing was interrupted due to cardiac ischemia or mesenteric ischemia.

Subjects in the Retrospective Control Group:

The dose and method of administration for Midodrine/Octreotide (M&O), albumin, or other vasopressor will be recorded as noted in the patient's medical record. To be included as a completed subject in this study, patients must have been treated for at least 48 hours with albumin infusions beyond volume resuscitation and diuretic withdrawal. Vasopressors also need to be used for a minimum of 48 hours.

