14.12 Reporting Serious or Unexpected Adverse Reactions or Adverse Events

Site Reporting to Sponsor

**Collaborative Research Study, Version 4: 06/29/21
To Treat HRS-AKI Patients with Continuous Terlipressin Infusion**

Investigators must report all SAEs to the sponsor (and applicable IRB) whether or not the events are study drug-related or expected.

All SAEs must be reported on a SAE form and faxed/scanned to International HealthCare (IHC) within **24 hours** of an investigator becoming aware of the event:

IHC Safety Review Officer
Email: [contact]

The initial SAE form does not need to be signed by the investigator; however, a signed SAE form is required for final SAE reporting. The initial scan by the investigator will include (whenever possible) a detailed description of the event including start and stop dates, causality assessment by the investigator, and supported as needed with written copies of medical records, autopsy reports, and other appropriate documents. Follow-up information (including information requested by the sponsor) should be reported by fax/scan within 24 hours of availability. The investigator is expected to make every effort to collect follow up information for each SAE in a timely fashion after the initial reporting of the SAE.

If there are any specific questions regarding a SAE classification, the investigator should contact the lead sponsor Principal Investigator for this study.

If there are any specific questions regarding the completion of the SAE form, please contact your site monitor.

Site Reporting to Institutional Review Board/Independent Ethics Committee

The investigator must notify the local IRB which approved the trial of the event in accordance with applicable guidelines.

Sponsor Reporting to Regulatory Authorities and Investigators

All reportable SAEs, including narrative safety reports of overall findings or data from aggregate analyses, will be reported to the applicable regulatory authorities by the sponsor or designee in accordance with the local regulations as described in the safety review plan for this study. The reporting of SAEs will be conducted in accordance with ICH E2A (Clinical Safety Data Management: Definitions and Standards for expedited reporting) and regulatory guidelines.

In addition, study endpoints described in Section 5.1 of the protocol that are serious adverse events will only be reported in the final clinical study report unless the event was unusual,

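### Section 15.4 tabulates SAEs by uncoded site term and investigator attribution, and section 15 defines no all-cause count of patients for the conditions on which the protocol itself restricts dosing

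*Combined protocol and SAP*

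**What the plan says.** Section 15.4 (Safety Variables) rules out coding: "Serious Adverse events will be not classified by Medical Dictionary for Drug Regulatory Activities (MedDRA) system organ class", nor by preferred term, severity or seriousness. The sentence that follows sets the replacement: "SAEs will be summarized using site reported terminology", together with the investigator's assessment of relationship to study drug. The phrasing of the first sentence is awkward, but the second shows that no coding is intended.

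Elsewhere the protocol picks out particular conditions. Section 8.4 says the drug should not be used in severe coronary artery disease or "in the setting of circulatory overload, pulmonary edema, or bronchospasm as determined by the Investigator", and lets the investigator hold the dose on the same grounds. It also bars restarting after an interruption for cardiac or mesenteric ischemia. The synopsis goes further for those two: "Dosing must be permanently discontinued if an event of cardiac ischemia or mesenteric ischemia occurs".

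Collection is broad on cause and narrow on type. Section 14.12 states: "Investigators must report all SAEs to the sponsor (and applicable IRB) whether or not the events are study drug-related or expected". Section 14 limits collection to SAEs, in the prospective terlipressin group only. For that group the synopsis says "the active treatment period will be up to 14 days, allowing 1 retreatment cycle". Section 14.12 also mentions "narrative safety reports of overall findings or data from aggregate analyses", handled under a safety review plan that is not provided.

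**The concern.** The primary objective covers safety as well as efficacy, and about 50 patients at 5-10 sites will be treated. The natural safety question is how many of them had a serious event of each kind that the protocol guards against. A table by site wording need not answer it. Sites may describe the same condition differently, one patient may appear under more than one term, and one patient may contribute in both the first course and the retreatment. Adding the rows can overcount patients, and reading them singly can understate the condition.

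The other summary dimension, attribution, does not fill the gap. No SAEs are collected in the retrospective controls, so investigator judgments cannot be set against a control rate. A count of patients regardless of cause does not depend on those judgments, and the reports needed for it will already be in hand.

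**Working it through.** **Step 1. Does section 15 define such a count anywhere?**

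| Place | What it gives | Grouped all-cause patient count for these conditions? |
|---|---|---|
| 15.2 | An incidence formula, set out for dialysis, mortality and transplant | No |
| 15.4 | SAEs by site term and by relationship; all deaths; optional vital signs, MELD, encephalopathy score, laboratory values | No. All deaths is cause-independent but is not one of the conditions |
| 15.5 | Completion status, reasons for discontinuation, exposure, deviations | Indirect at best: may show the two ischemic stops, depending on how reasons are recorded |
| 15.6 | A denominator: everyone with at least one dose | No numerator is defined for it |

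The plan states no figure on this point, so there is none to reproduce.

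**Step 2. What can a term table pin down? (illustration)**

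Inputs: n = 50, the planned number treated (6.1, 7.2). The event counts are assumptions, because the documents give no event rate.

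Suppose three site terms all describe overload or pulmonary edema and each row shows 2 patients. If the same 2 patients fill every row, 2 patients are affected. If no patient repeats, 2 + 2 + 2 = 6 are. Enumerating all ways to fill the rows gives 2, 3, 4, 5 or 6 distinct patients.

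Exact (Clopper-Pearson) 95% interval for x of n: the lower limit is the 0.025 quantile of Beta(x, n-x+1), and the upper limit is the 0.975 quantile of Beta(x+1, n-x).

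| Patients affected | Rate (x/50) | Exact 95% CI |
|---|---|---|
| 2 | 4.0% | 0.5-13.7% |
| 3 | 6.0% | 1.3-16.5% |
| 4 | 8.0% | 2.2-19.2% |
| 5 | 10.0% | 3.3-21.8% |
| 6 | 12.0% | 4.5-24.3% |

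The same printed rows are thus compatible with a threefold range (12.0/4.0). The factor of three comes from the choice of three non-overlapping or fully overlapping rows.

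**Step 3. Does the group boundary matter? (illustration)**

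Assume 3 patients with overload or pulmonary edema: 3/50 = 6.0% (1.3-16.5%). Assume 4 other patients reported only as respiratory failure or dyspnea. Including them gives 7/50 = 14.0% (5.8-26.7%). This is why the mapping should be set beforehand and the group shown both ways.

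**Step 4. What would zero events show?**

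The upper limit is 1 - 0.025^(1/n): 7.1% at n = 50, 8.8% if 40 are treated, 6.0% if 60. Without an interval, a group with no events invites over-reading.

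**The case against.** The case on the other side is substantial.

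- **Leaving SAEs uncoded is a deliberate choice** in a small, descriptive, SAE-only safety review. That stands, and the remedy does not ask for MedDRA coding.
- **The data are not lost.** SAE forms carry event descriptions, the synopsis permits analyses beyond those specified, and with about 50 patients the count could be rebuilt from a patient-level listing. True. But 15.4 specifies no listing, and grouping terms after seeing them is what a rule fixed beforehand avoids.
- **The safety review plan may already group events.** This cannot be excluded. A reader might infer that the trial has no grouped safety analysis at all; the documents support only the statement that section 15 defines none.
- **Discontinuation reasons in 15.5 may reveal the ischemic events.** Possibly, but they omit the other conditions.
- **An uncontrolled rate does not separate drug from disease, and non-serious events are not collected.** Both are correct and govern how the table must be labelled.

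Two stronger readings are tempting. One is that 8.4 declares pulmonary edema a drug effect. It does not: it is a precaution on use with discretion over escalation, and only the two ischemic events carry a permanent stop. The other concerns Table 4 in 14.5, whose respiratory entries run "Dyspnea Epistaxis Pulmonary edema Respiratory failure". A reader might infer that the listing systematically biases attribution, or conversely that it can never make an event unrelated. Neither follows. The table is optional guidance and the causality criteria are permissive. An event with neither suggestive timing nor a known response pattern meets only one of the items for a possible relationship even when the clinical state explains it, so it can be called unrelated if the investigator judges disease clearly to be the cause. Other combinations can move it differently. The documents do not settle the direction, so no change to 14.5 is warranted here.

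**Conclusion.** The point holds as a minor one. As written, 15.4 can scatter the conditions the protocol acts on over several verbatim rows, and section 15 defines no all-cause patient count that would bring them together. This rests on the text of section 15 alone; if the safety review plan contains a grouping, a cross-reference from 15.4 would close the matter. No efficacy analysis and no planned safety comparison is affected. The real size is unknown. The range of 4.0% to 12.0%, and the shift from 6.0% to 14.0% with the group boundary, depend on assumed counts and show only what a term table can leave undetermined.

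**What to change.** Add to 15.4 one descriptive, all-cause table in the safety population. It gives the number and percentage of patients with at least one SAE in each group, with an exact 95% CI, each patient counted once per group across the first course and any retreatment. The groups:

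1. circulatory overload or pulmonary edema, shown without and with respiratory failure and dyspnea;
2. bronchospasm;
3. cardiac ischemia;
4. mesenteric ischemia.

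Write the mapping from terms to groups before SAEs are tabulated. Assign any new site term without sight of the investigator's attribution, and show attribution alongside. Label the result an SAE rate and note that, without a control, it does not separate drug from disease.

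The cost is one table, a short term list and some work to group site terms, all from SAEs already collected. The grouped rates may look less favourable than the separate rows.
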